6.3. Protocol Deviation (SS)

Table14 Protocol Deviation

Item	Indicator	Experimental		Total
		Group	Control Group	
Protocol Deviations Occurred	None n(%)			
	Yes n(%)			
	Total (Missing)			

Item	Indicator	Experimental Group	Control Group	Total
		Statistic		
	P-value			

6.4. Anticoagulant and Antiplatelet Medication Use (SS)

Table15 Anticoagulant use during screening period

Item	Indicator	Experimental Group	Control Group	Total
Warfarin	Yes n(%)			
	No n(%)			
	Unknown n(%)			
	Total (Missing)			
	Statistic			
	P-value			
Low molecular weight heparin	Yes n(%)			
	No n(%)			
	Unknown n(%)			
	Total (Missing)			
	Statistic			
	P-value			
Unfractionated heparin	Yes n(%)			
	No n(%)			
	Unknown n(%)			
	Total (Missing)			
	Statistic			
	P-value			
Urokinase	Yes n(%)			
	No n(%)			
	Unknown n(%)			
	Total (Missing)			
	Statistic			
	P-value			
Other anticoagulants	Yes n(%)			
	No n(%)			
	Unknown n(%)			
	Total (Missing)			
	Statistic			
	P-value			

Table16 Antiplatelet Drugs During Screening Period

Item	Indicator	Experimental Group	Control Group	Total
Aspirin	Yes n(%)			
	No n(%)			
	Unknown n(%)			
	Total (Missing)			
	Statistic			
	P-value			
Clopidogrel	Yes n(%)			
	No n(%)			
	Unknown n(%)			
	Total (Missing)			
	Statistic			
	P-value			
Cilostazol	Yes n(%)			
	No n(%)			
	Unknown n(%)			
	Total (Missing)			
	Statistic			
	P-value			
Other Antiplatelet Agents	Yes n(%)			
	No n(%)			
	Unknown n(%)			
	Total (Missing)			
	Statistical measure			
	P-value			

Table17 Anticoagulants on the day of surgery

Item	Indicator	Experimental Group	Control Group	Total
Warfarin	Yes n(%)			
	No n(%)			
	Unknown n(%)			
	Total (Missing)			
	Statistic			
	P-value			
Low molecular weight heparin	Yes n(%)			
	No n(%)			
	Unknown n(%)			
	Total (Missing)			
	Statistic			
	P-value			

Item	Indicator	Experimental Group	Control Group	Total
Unfractionated heparin	Yes n(%)			
	No n(%)			
	Unknown n(%)			
	Total (Missing)			
	Statistic			
	P-value			
Urokinase	Yes n(%)			
	No n(%)			
	Unknown n(%)			
	Total (Missing)			
	Statistic			
	P-value			
Other anticoagulants	Yes n(%)			
	No n(%)			
	Unknown n(%)			
	Total (Missing)			
	Statistic			
	P-value			

Table18 Antiplatelet Medication on the Day of Surgery

Item	Indicator	Experimental Group	Control Group	Total
Aspirin	Yes n(%)			
	No n(%)			
	Unknown n(%)			
	Total (Missing)			
	Statistic			
	P-value			
Clopidogrel	Yes n(%)			
	No n(%)			
	Unknown n(%)			
	Total (Missing)			
	Statistic			
	P-value			
Cilostazol	Yes n(%)			
	No n(%)			
	Unknown n(%)			
	Total (Missing)			
	Statistic			
	P-value			
Other	Antiplatelet	Yes n(%)		

Item	Indicator	Experimental		Total
		Group	Control Group	
Agents	No n(%)			
	Unknown n(%)			
	Total (Missing)			
	Statistical measure			
	P-value			

Table19 Postoperative Anticoagulants

Item	Indicator	Experimental Group	Control Group	Total
Warfarin	Yes n(%)			
	No n(%)			
	Unknown n(%)			
	Total (Missing)			
	Statistic			
	P-value			
Low molecular weight heparin	Yes n(%)			
	No n(%)			
	Unknown n(%)			
	Total (Missing)			
	Statistic			
	P-value			
Unfractionated heparin	Yes n(%)			
	No n(%)			
	Unknown n(%)			
	Total (Missing)			
	Statistic			
	P-value			
Urokinase	Yes n(%)			
	No n(%)			
	Unknown n(%)			
	Total (Missing)			
	Statistic			
	P-value			
Other anticoagulants	Yes n(%)			
	No n(%)			
	Unknown n(%)			
	Total (Missing)			
	Statistic			
	P-value			

Table20 Postoperative Antiplatelet Therapy

Item	Indicator	Experimental Group	Control Group	Total
Aspirin	Yes n(%)			
	No n(%)			
	Unknown n(%)			
	Total (Missing)			
	Statistic			
	P-value			
Clopidogrel	Yes n(%)			
	No n(%)			
	Unknown n(%)			
	Total (Missing)			
	Statistic			
	P-value			
Cilostazol	Yes n(%)			
	No n(%)			
	Unknown n(%)			
	Total (Missing)			
	Statistic			
	P-value			
Other Antiplatelet Agents	Yes n(%)			
	No n(%)			
	Unknown n(%)			
	Total (Missing)			
	Statistical measure			
	P-value			

6.5. Surgical Record (FAS)

Table21 Target Vessel Surgery Information

Item	Indicator	Experimental Group	Control Group	Total
Number of Target Vessels*	1 n(%)			
	2 n(%)			
	Total (Missing)			
	Statistic			
	P-value			
Number of devices used	1 n(%)			
	2 n (%)			
	Total (Missing)			
	Statistic			
	P-value			

Item	Indicator	Experimental Group	Control Group	Total
Number of Thrombectomy Procedures	N(Missing)			
	Mean (SD)			
	Median			
	Q1, Q3			
	Min,Max			
	Statistic			
	P-value			
Number of Thrombectomy Procedures - Qualitative	1 time n(%)			
	2 times n(%)			
	≥3 times n(%)			
	Total (Missing)			
	Statistic			
	P-value			
Distal Embolism	Yes n(%)			
	No n(%)			
	Total (Missing)			
	Statistic			
	P-value			
Whether underlying stenosis was detected after recanalization	Yes n(%)			
	No n(%)			
	Total (Missing)			
	Statistic			
	P-value			
Use of Recute or Other Auxiliary Therapy	Yes n(%)			
	No n(%)			
	Total (Missing)			
	Statistic			
	P-value			
Stent implantation for recute treatment	Yes n(%)			
	No n(%)			
	Total (Missing)			
	Statistic			
	P-value			
Use of Balloon Dilatation for Recute Treatment	Yes n(%)			
	No n(%)			
	Total (Missing)			
	Statistic			
	P-value			
Other Recute Treatments Used	Yes n(%)			
	No n(%)			
	Total (Missing)			

Item	Indicator	Experimental Group	Control Group	Total
	Statistic			
	P-value			

Note: Except for analyses where the number of target vessels is the subject unit, all other analyses in this table use target vessel units.

Table22 Thrombectomy Device Usage Information (Device Units)

Item	Indicator	Experimental Group	Control Group	Total
Stent Diameter (mm)	N(Missing)			
	Mean(SD)			
	Median			
	Q1, Q3			
	Min,Max			
	Statistic			
	P-value			
Stent Length (mm)	N(Missing)			
	Mean(SD)			
	Median			
	Q1, Q3			
	Min,Max			
	Statistic			
	P-value			
Device Specifications (Diameter × Length) (mm × mm)	3×20 n(%)			
	3×30 n(%)			
	3×40 n(%)			
	4×15 n(%)			
	4×20 n(%)			
	4×30 n(%)			
	4×40 n(%)			
	6×20 n(%)			
	6×30 n(%)			
	6×40 n(%)			
	Total (Missing)			
	Statistic			
	P-value			

6.6. Efficacy Endpoints

6.6.1. Primary Efficacy Endpoints- core laboratory

Table23 Immediate Postoperative Revascularization Rate

Item	Indicator	FAS		PPS	
		Experimental Group	Control Group	Experimental Group	Control Group
Immediate Postoperative Revascularization Rate	Recanalization n(%)				
	Non-recanalization n(%)				
	Total (Missing)				
	Statistic				
	P-value				
Immediate postoperative mTICI classification	Grade 0 n(%)				
	Grade 1 n(%)				
	Grade 2a n(%)				
	Grade 2b n(%)				
	Grade 3 n(%)				
	Total (Missing)				
	Statistic (CMH)				
	P-value				

Note 1: Target vessel recanalization, mTICI grade 2b or 3. The same applies below.

Note 2: The 95% confidence interval for the single-group success rate was calculated using the Clopper-Pearson method.

Note 3: For subjects with missing immediate postoperative recanalization rates in FAS, worst-case imputation was applied, treating them as having failed to achieve immediate recanalization. The same applies below.

Note 4: Analysis of immediate postoperative recanalization and mTICI classification based on external data: XX.

Table24 Hypothesis Testing for Immediate Postoperative Recanalization Rate

Population	Indicator	Treatment Group n(%)	Control Group n(%)	Difference in Rates Between Groups	Difference in Rates Between Groups Two-Sided 95% CI	P-value	Non-inferiority margin
FAS	Immediate postoperative revascularization rate						-12.5%
PPS	Immediate postoperative revascularization rate						-12.5%

Note 1: Rate difference = experimental group - control group. Non-inferiority margin set at -10%. The 95%

confidence interval for the rate difference was calculated using the exact probability method.

Note 2: The lower limit of the 95% confidence interval for the difference in patency success rates between groups exceeded -12.5%, confirming non-inferiority.

Table25 Immediate Postoperative Vascular Recanalization Rates by Center

Center ID	Item	Indicator	FAS		PPS	
			Experimental Group	Control Group	Experimental Group	Control Group
01	Immediate Vascular Rate	Postoperative Recanalizationn(%) Non-recanalization n(%) Total (Missing)				
02	Immediate Vascular Rate	Postoperative Recanalizationn(%) Non-recanalization n(%) Total (Missing)				
03	Immediate Vascular Rate	Postoperative Recanalizationn(%) No recanalization n(%) Total (Missing)				
.....	Immediate Vascular Rate	Postoperative Recanalizationn(%) No recanalization n(%) Total (Missing)				

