7.2. Calculation of Sample Size

7.2.1. Total Sample Size

The primary endpoint of the study is the success rate of recanalization, using non-inferiority test. A total of 220 patients are planned to be enrolled and randomly assigned to the test or control group in a 1:1 ratio, with 110 subjects in each group. mTICI can reach 76% at 6-16h according to DEFUSE-3 and 84% at 6-24h according to DAWN. Within 6 h, mTICI is 86% in EXTEND-IA, 88% in SWIFT PRIME, and 87% in PISTE.

According to the estimation combined with the existing clinical evidence and the experience of clinical experts, assuming that the recanalization success rate after treatment is 89% in both the test group and control group within 24h ^[10-19], the non-inferiority margin is set at 12.5% after discussion between the clinical investigator and the sponsor. When the significance level α of statistical test is set as one-sided 0.025 and the power $1-\beta$ is set as 80%, the sample size is calculated as 99 in each group. In consideration of the maximum possible dropout rate of 10% in the study, the sample size in each group is 110. Therefore, 220 subjects are required in total. It is calculated according to statistical principles that,

the corresponding sample size formula is:

$$n_T = n_C = \frac{(Z_{1-\alpha/2} + Z_{1-\beta})^2 [P_C(1 - P_C) + P_T(1 - P_T)]}{(|D| - \Delta)^2}$$

where, n_T and n_C are the respective sample size of the test group and control group; $Z_{1-\alpha/2}$ and $Z_{1-\beta}$ are the percentiles in standard normal distribution; P_T is the expected success rate of recanalization in the test group, P_C is the expected success rate of recanalization in the control group; $|D|$ is the absolute value of the

difference between groups in the expected recanalization, $|D| = |P_T - P_C|$; Δ is the non-inferiority margin (taking the negative value).

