8.2. Pass/Fail Criteria for Clinical Trial Results

If the lower limit of the 95% CI of the difference in recanalization success rate between the test group and control group is greater than -12.5% (the pre-specified non-inferiority margin), and there are no clinically unacceptable safety issues related to the investigational device, the study is qualified, otherwise it is unqualified.

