5.4. Efficacy Analysis

5.4.1. Primary Efficacy

Primary efficacy evaluation is based on the Full Analysis Set (FAS) and the Per-Protocol Set (PPS).

This trial employs a prospective, multicenter, randomized controlled design with a non-inferiority comparison. It demonstrates that the investigational device meets clinical application requirements by comparing it with an approved comparator. The primary endpoint evaluates intraoperative vascular recanalization success rate, with the corresponding statistical hypothesis test defined as:

$$H_0 : p_T - p_C \leq -\Delta$$

$$H_1 : p_T - p_C > -\Delta$$

In the formula, P_T represents the expected recanalization success rate in the test group, P_C denotes the expected recanalization success rate in the control group, and $-\Delta$ indicates the non-inferiority margin of -12.5%.

The target vessel recanalization rates between the test and control groups will be compared, and the 95% confidence interval (CI) for the rate difference between the two groups will be calculated. If the lower limit of the 95% CI for the rate difference is greater than -12.5%, the test group will be considered non-inferior to the control group. The intergroup comparison will employ a CMH chi-square analysis adjusted for center effects.

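### A note to the SAP's primary-result tables gives a non-inferiority margin of -10%, against the -12.5% used everywhere else

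*SAP*

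**What the plan says.** The margin is stated in many places, and all but one pair agree.

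- Protocol 7.2.1: "the non-inferiority margin is set at 12.5% after discussion between the clinical investigator and the sponsor".
- Protocol 7.1.2.3 applies -12.5% to the lower confidence limit, and Protocol 8.2 makes this the pass/fail criterion: the lower limit must be such that it "is greater than -12.5% (the pre-specified non-inferiority margin").
- SAP 1.5 repeats 12.5% in the sample-size section. SAP 5.4.1 opens its decision rule with "If the lower limit of the 95% CI for the rate difference is greater than -12.5" (per cent).
- SAP Table 24 (core laboratory, section 6.6.1) and Table 27 (EDC, section 6.6.2) print -12.5% in the margin column for both FAS and PPS. Note 2 to each table ties the non-inferiority conclusion to -12.5%.
- Note 1 to each of these two tables reads "Rate difference = experimental group - control group. Non-inferiority margin set at -10" (per cent).

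The same Note 1 also names the method for the confidence interval of the rate difference (an exact method), which SAP 5.4.1 does not specify.

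**The concern.** The margin is the trial's pass/fail threshold. A lower confidence limit above -12.5% but not above -10% passes by Note 2 and fails by Note 1 of the same table.

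Note 1 cannot be skipped as boilerplate, because whoever programs the table needs it for the interval method. The tables also have a P-value column. If that is a non-inferiority P-value, it depends on the margin coded, so a program using -0.10 could print a P-value that disagrees with the interval verdict beside it.

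Operators know which device they are using. If the SAP still carries two margins when the database is locked, the sponsor can be asked which one was intended, and the answer would then come after the result is known.

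**Working it through.** **Inputs, all from Protocol 7.2.1**

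- Success rates: "assuming that the recanalization success rate after treatment is 89% in both the test group and control group within 24h", so the true difference is 0.
- Significance level: "of statistical test is set as one-sided 0.025", so z = 1.96.
- Power and evaluable number: "is set as 80%, the sample size is calculated as 99 in each group", so z = 0.8416 for 80% power.
- Dropout: "In consideration of the maximum possible dropout rate of 10% in the study, the sample size in each group is 110".

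**Step 1. Reproduce the plan's sample size.** With a true difference of zero and margin d, the plan's formula becomes n = (1.96 + 0.8416)² × 2 × 0.89 × 0.11 / d².

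The numerator is 7.849 × 0.1958 = 1.537.

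| Margin d | n per arm | Rounded up | After 10% dropout (n / 0.9) |
|---|---|---|---|
| 0.125 | 1.537 / 0.015625 = 98.4 | 99 | 110 per arm, 220 in total |
| 0.10 | 1.537 / 0.01 = 153.7 | 154 | 172 per arm, 344 in total |

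The stated 99, 110 and 220 follow exactly from 12.5%. A 10% margin does not give 99 even at a one-sided level of 0.05, where n would be 122.

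**Step 2. Power of the planned trial at each margin.** Power = Φ(d / SE - 1.96), with SE = √(2 × 0.89 × 0.11 / n).

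| n per arm | SE | Power at d = 0.125 | Power at d = 0.10 |
|---|---|---|---|
| 99 | 0.0445 | 80.3% | 61.4% |
| 110 | 0.0422 | 84.2% | 65.9% |

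**Step 3. How often the two margins disagree.** All pairs of binomial outcomes were enumerated with both true rates at 89%. The table gives the probability of passing at -12.5% and failing at -10%.

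| n per arm | Wald interval | Score test |
|---|---|---|
| 99 | 18.3% | 19.5% |
| 110 | 18.2% | 17.9% |

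If the true test rate is 85% or 87% instead (an assumption outside the plan) and control stays at 89%, the Wald figures run from 18% to 22%.

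**Step 4. A concrete result.** Take 95/110 in the test arm and 98/110 in the control arm. The difference is -2.7 points and the Wald lower limit is -11.4%, which passes at -12.5% and fails at -10%. With control at 98/110, the smallest passing test count is:

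| Method | At -12.5% | At -10% |
|---|---|---|
| Score test | 95 | 97 |
| Wald interval | 94 | 97 |

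**The case against.** The strongest reply is that the plan has only one decision rule. Protocol 8.2 and SAP 5.4.1 both state it with -12.5%, the margin column and Note 2 agree, and Note 1 attaches no verdict to its figure. On that reading -10% is a single slip copied into two table shells, and opposite verdicts arise only if someone puts a table note above every operative rule. Protocol V3.0, dated February 9, 2022, already fixes 12.5%. Protocol 8.5 says the main analysis principles and methods should in principle not be changed. The stray figure is also the stricter one, so applying it could not raise the false-positive rate. Recanalization is read blind by a central laboratory, whose reading prevails on disagreement. No program using -0.10 has been seen.

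Most of this stands. The -10% does look like a drafting error, and the power loss and the disagreement rate are conditional on someone applying it. The cut-offs in Step 4 are not those of the SAP either: Note 1 names an exact interval and SAP 5.4.1 a centre-adjusted CMH analysis, so the counts would move a little.

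It does not remove the point. A wrong threshold in the tables that report the primary result is more than an editorial matter, and the zone between the two margins exists under any interval method. Blinded reading protects the outcome assessment. It does not settle which margin was pre-specified.

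**Conclusion.** The concern holds. Note 1 of SAP Tables 24 and 27 contradicts the margin stated in the rest of the SAP and in the protocol, and must be corrected. The intended margin is not in doubt, because 99 evaluable and 110 randomized per arm follow only from 12.5%.

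If -10% were applied, power at 110 per arm would fall from 84% to 66%. About 18% to 20% of trials of equally effective devices would have their verdict reversed. These figures assume 89% success in both arms and Wald or score methods in place of the SAP's exact interval and centre-adjusted analysis.

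**What to change.** 1. In Note 1 of SAP Tables 24 and 27, replace -10% with -12.5%.
2. Check that the program for both tables, including any non-inferiority P-value, uses -0.125.
3. Record the correction, with its date, before database lock. Protocol 8.5 already requires SAP modifications to be recorded.

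The cost is one figure in each of two notes and a short program check. Sample size, hypotheses and the decision rule stay as they are.

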6.6.2. Primary Efficacy Endpoint - EDC

Table26 Immediate Postoperative Revascularization Rate

Item	Indicator	FAS		PPS	
		Experimental Group	Control Group	Experimental Group	Control Group
Immediate Revascularization Rate	Postoperative Recanalizationn(%)				

Item	Indicator	FAS		PPS	
		Experimental Group	Control Group	Experimental Group	Control Group
Immediate postoperative mTICI classification	Non-recanalization				
	n(%)				
	Total (Missing)				
	Statistic				
	P-value				
	Grade 0 n(%)				
	Grade 1 n(%)				
	Grade 2a n(%)				
	Grade 2b n(%)				
	Grade 3 n(%)				
	Total (Missing)				
	Statistic (CMH)				
	P-value				

Note 1: Target vessel recanalization, mTICI grade 2b or 3. Same applies below.

Note 2: The 95% confidence interval for the single-group success rate was calculated using the Clopper-Pearson method.

Note 3: For missing immediate post-procedural recanalization rates in the FAS, worst-case imputation was applied, treating missing values as non-achievement of immediate recanalization. The same applies below.

Table27 Hypothesis Test for Immediate Postoperative Vascular Recanalization Rate

Population	Indicator	Experimental Group n(%)	Control Group n(%)	Difference in Rates Between Groups	Difference in Rates Between Groups Two-sided 95% CI	P-value	Non-inferiority margin
FAS	Immediate postoperative revascularization rate						-12.5%
PPS	Immediate postoperative revascularization rate						-12.5%

Note 1: Rate difference = experimental group - control group. Non-inferiority margin set at -10%. The 95% confidence interval for the rate difference was calculated using the exact probability method.

Note 2: The lower limit of the 95% confidence interval for the difference in patency success rates between groups exceeded -12.5%, confirming non-inferiority.

Table28 Immediate Postoperative Vascular Recanalization Rates by Center

Center ID	Item	Indicator	FAS		PPS	
			Experimental Group	Control Group	Experimental Group	Control Group
01	Immediate Vascular Rate	Postoperative Recanalizationn(%) Non-recanalization n(%) Total (Missing)				
02	Immediate Vascular Rate	Postoperative Recanalizationn(%) No recanalization n(%) Total (Missing)				
03	Immediate Vascular Rate	Postoperative Recanalizationn(%) No recanalization n(%) Total (Missing)				
.....	Immediate Vascular Rate	Postoperative Recanalizationn(%) No recanalization n(%) Total (Missing)				

6.6.3. Secondary efficacy endpoint

Table29 mRS 0-2 at 90 days post-surgery

Item	Indicator	FAS		PPS	
		Experimental Group	Control Group	Experimental Group	Control Group
mRS 0-2 at 90 days post-surgery	Yes n(%)				
	No n(%)				
	Total (Missing)				
	Statistic (CMH)				
	P-value				
90-day postoperative mRS	Grade 0 n(%)				
	Grade 1 n(%)				
	Grade 2 n(%)				
	Grade 3 n(%)				

Item	Indicator	FAS		PPS	
		Experimental Group	Control Group	Experimental Group	Control Group
	Grade 4 n(%)				
	Level 5 n(%)				
	Level 6 n(%)				
	Total (Missing)				
	Statistic				
	P-value				

Table30 Recanalization Time

Item	Indicator	FAS		PPS	
		Experimental Group	Control Group	Experimental Group	Control Group
Recanalization Time (min)	N(Missing)				
	Mean(SD)				
	Median				
	Q1, Q3				
	Min, Max				
	Statistic				
	P-value				

Note: Time to reperfusion = End time - Femoral artery puncture time (If reperfusion is successful, the end time is the time of successful reperfusion; if reperfusion fails, the end time is recorded as the time of surgical completion).

Table31 Postoperative NIHSS Score Improvement

Item	Indicator	FAS		PPS	
		Experimental Group	Control Group	Experimental Group	Control Group
Preoperative NIHSS Score	N(Missing)				
	Mean(SD)				
	Median				
	Q1, Q3				
	Min,Max				
	Statistic				
	P-value				
NIHSS score at 24±12 hours postoperatively	N(Missing)				
	Mean(SD)				
	Median				
	Q1, Q3				
	Min,Max				
	Statistic				
	P-value				

Item	Indicator	FAS		PPS	
		Experimental Group	Control Group	Experimental Group	Control Group
NIHSS score reduction >4 points (postoperative 24±12 h vs. preoperative)	Yes n(%)				
	No n(%)				
	Total (Missing)				
	Statistic				
NIHSS score at 7±2 days post-op/prior to discharge	P-value				
	N(Missing)				
	Mean (SD)				
	Median				
	Q1, Q3				
	Min,Max				
	Statistic				
Proportion of subjects with NIHSS score reduction >4 points (7 ± 2 days post-op/prior to discharge)	P-value				
	Yes n(%)				
	No n(%)				
	Total (Missing)				
	Statistic				
	P-value				

Table32 Device Operation Success Rate (per device unit)

Item	Indicator	FAS	PPS
Whether Device Operation Was Successful	Yes n(%)		
	No n(%)		
	Total (Missing)		

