3.2. Contents

The study is a prospective, multicenter, randomized controlled, non-inferiority clinical trial, of which the investigational device is Sinomed Neurovita Ghunter Revascularization Device and the control device is Solitaire FR (hereinafter referred to as the control product under the trade name Solitaire FR) distributed by Covidien Healthcare International Trading (Shanghai) Co., Ltd.; the study is planned to be conducted in more than 10 sites and include 220 subjects. The subjects who meet the inclusion criteria will be randomized into the test group or control group in 1:1. The study is to collect and evaluate whether the success rate of instant recanalization is not inferior to Solitaire FR when Sinomed Neurovita Ghunter Revascularization Device is used for endovascular treatment of acute ischemic stroke, and to evaluate whether there is a statistically significant difference in the proportion of subjects with mRS score of 0 - 2 on 90d postoperatively, the time from femoral artery puncture to recanalization/the end time of operation for subjects whose recanalization failed, the proportion of subjects with NIHSS score decrease > 4 , and the success rate of device operation as compared with Solitaire FR when Ghunter Revascularization Device is used for endovascular treatment of acute ischemic stroke. Also, whether there is statistical difference in incidence of symptomatic intracranial hemorrhage within 24h postoperatively, all-cause mortality within 90d, incidence of SAE, incidence of AE, and incidence of device defects between Ghunter Revascularization Device and Solitaire FR for endovascular treatment of acute ischemic stroke will be evaluated.

4. Background of Clinical Trial

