1.3. Study Design

This is a prospective, multicenter, randomized controlled, non-inferiority clinical trial. The investigational device is the Intracranial Thrombectomy Stent (Sino Neurovita), with the comparator device being the Solitaire FR (Covidien Medical Device International Trading (Shanghai) Co., Ltd., hereinafter referred to by its trade name Solitaire FR). The trial is planned to be conducted at more than 10 clinical trial sites, enrolling 220 subjects. Eligible subjects were randomized 1:1 to either the study group or control group. The study evaluated whether the immediate recanalization rate of the Sinomed Neurovita Intracranial Thrombectomy Stent was non-inferior to that of the Solitaire FR when used for endovascular treatment of acute ischemic stroke. A central reading laboratory independent of the trial conducted blinded assessments of target vessel recanalization. The study evaluated whether there were statistically significant differences between the Sinomed Neurovita Intracranial Thrombectomy Stent and the Solitaire FR in the following outcomes for acute ischemic stroke endovascular therapy: 90-day mRS 0-2 rate, time from femoral artery puncture to recanalization or

procedure end time for non-recanalized subjects, proportion of subjects with NIHSS improvement ≥ 4 points, and device procedural success rate. Evaluate whether there are statistically significant differences between the Sinomed Neurovita Intracranial Thrombectomy Stent and Solitaire FR in the following outcomes for endovascular treatment of acute ischemic stroke: incidence of symptomatic intracranial hemorrhage within 24 hours post-procedure, all-cause mortality within 90 days, incidence of serious adverse events (SAE), incidence of adverse events (AE), and incidence of device failure.

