1.5. Sample Size

The primary endpoint of this trial is the success rate of recanalization. It adopts a prospective, multicenter, randomized controlled design, with a non-inferiority test.

Based on existing clinical evidence and expert consensus, the pre-specified non-inferiority margin was set at 12.5%, assuming both groups achieved an 89% recanalization rate within 24 hours. With a one-sided significance level α of 0.025 and a power $(1-\beta)$ of 80%, the calculated sample size per group is 99 subjects. Considering a maximum possible 10% dropout rate, the sample size per group is increased to 110 subjects, totaling 220 subjects. Based on statistical principles,

The corresponding sample size formula is:

$$n_T = n_C = \frac{(Z_{1-\alpha/2} + Z_{1-\beta})^2 [P_C(1 - P_C) + P_T(1 - P_T)]}{(|D| - \Delta)^2}$$

In the formula, n_T and n_C are the respective sample size of the test group and control group; $Z_{1-\alpha/2}$ and $Z_{1-\beta}$ are the percentiles in standard normal distribution; P_T is the expected success rate of recanalization in the test group, P_C is the expected success rate of recanalization in the control group; $|D|$ is the absolute value of the difference between groups in the expected recanalization, $|D|=|P_T-P_C|$; Δ is the non-inferiority margin (taking the negative value).

This trial will be conducted simultaneously across multiple clinical trial sites. Considering feasibility and enrollment progress, the enrollment quotas for each participating site will be adjusted based on actual circumstances to ensure balanced enrollment across centers. The final enrollment size

for any single site should not exceed 50% of the total number of cases.

2. Evaluation Endpoint

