2.1.2. Secondary efficacy endpoints

1. 90-day Postoperative mRS 0-2 Score Ratio: $\text{mRS 0-2 Score Ratio} = \text{Number of subjects with mRS 0-2 score at 90 days postoperatively} / \text{Number of subjects undergoing thrombectomy via intracranial thrombectomy device} \times 100\%$.
2. Time to recanalization: $\text{Time to recanalization} = \text{End time} - \text{Femoral artery puncture time}$ (If recanalization is successful, the end time is the time of successful recanalization; if no recanalization occurs, the end time is recorded as the time of procedure completion). Here, recanalization refers to successful target vessel recanalization with mTICI grade 2b or 3 following thrombectomy using the investigational device.
3. Postoperative NIHSS score improvement >4 points: Improvement in NIHSS score at 24 ± 12 hours postoperatively, 7 ± 2 days postoperatively/prior to discharge compared to baseline. $\text{Percentage of subjects with } >4\text{-point NIHSS improvement} = \text{Number of subjects in this group}$

with >4-point postoperative NIHSS improvement / Number of subjects in this group treated with thrombectomy via thrombotic stents $\times 100\%$.

4. Success rate of device operation: Defined as successful delivery of the device to the target lesion site, followed by accurate deployment and retrieval. Success rate of device operation = Number of devices successfully delivered, deployed, and retrieved in this group / Total number of devices used in this group $\times 100\%$.

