5.4.2. Secondary Endpoints

Secondary efficacy assessments were based on the full analysis set (FAS) and the per-protocol set (PPS).

The 90-day postoperative mRS 0-2 rate, the proportion of subjects with NIHSS improvement >4 points, and the device procedural success rate were analyzed as categorical data; recanalization time was analyzed as a quantitative endpoint.

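### The SAP Table 32 shell has no place to report the planned between-arm comparison of device operation success, and the planned test does not allow for more than one device per subject

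*SAP*

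**What the plan says.** Both documents set this endpoint up as a comparison of the two devices. Protocol 3.2 lists it among the outcomes to be tested for a statistically significant difference: "and the success rate of device operation as compared with Solitaire FR". SAP 1.3 says the same, opening its list of secondary outcomes, which includes device procedural success, with "The study evaluated whether there were statistically significant differences between the Sinomed Neurovita Intracranial Thrombectomy Stent and the Solitaire FR".

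SAP 2.1.2 (item 4) defines the rate within each group and counts devices: "Number of devices successfully delivered, deployed, and retrieved in this group / Total number of devices used in this group". The formula in protocol 6.1.6 is also per group and per device.

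On method, SAP 5.4.2 says that "the device procedural success rate were analyzed as categorical data", on both FAS and PPS. SAP 5.1 assigns a chi-square test, or an exact method where chi-square does not apply, to categorical comparisons between two groups, at two-sided 0.05.

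The output shell in SAP 6.6.3 is "Table32 Device Operation Success Rate (per device unit"). Its columns are FAS and PPS. Its rows are Yes, No and Total (Missing).

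A subject can contribute more than one device. SAP Table 21 has a row for "Number of devices used" with categories 1 and 2, which the table's note counts per target vessel. Protocol 6.2.2.4 allows a new device for a further attempt and requires one if the first is found damaged.

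**The concern.** There are two linked gaps.

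**The shell.** The text plans a comparison, but the table meant to carry the result has nowhere to put it. This is the secondary endpoint that most directly describes handling: delivery, deployment and withdrawal. A single rate per analysis set says nothing about whether the new device handles as reliably as the comparator.

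**The unit of analysis.** A chi-square or exact test on device counts assumes independent devices. Two devices used in one subject share that subject's anatomy, thrombus and operator. If a second device is opened because the first failed, the number of devices also depends on the outcome. Neither document gives a method for devices nested in subjects, so the choice could be left until the data have been seen.

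**Working it through.** **1. The plan's own figure.** The only sizing in the documents is for the primary endpoint, "assuming both groups achieved an 89% recanalization rate within 24 hours", with a margin of 12.5%, one-sided 0.025 and 80% power:

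n = (1.96 + 0.8416)² × 2 × 0.89 × 0.11 / 0.125² = 98.4, rounded up to 99; 99 / (1 − 0.10) = 110 per group, 220 in total.

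This reproduces. It is a subject-level calculation and does not bear on device operation success, for which no expected rate or power is given.

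**2. Table 32 beside its neighbours.**

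| Shell | Unit | Arm columns | Statistic and P-value rows |
|---|---|---|---|
| Tables 29–31 (other secondary endpoints) | subject | yes | yes |
| Table 22 (device usage) | device | yes | yes |
| Table 32 (device operation success) | device | no | no |

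Table 22 shows that counting devices is not a reason to drop the arms. Loss in PDF reading cannot be ruled out entirely. It is unlikely, because columns and rows would both have to vanish cleanly from one table while the adjacent tables survived.

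**3. What the shell could show if the arms were combined.** With equal device counts per arm, success of 90% vs 98%, 98% vs 90%, and 94% vs 94% all give 94%. As an invented example at one device per subject, 97/110 (88.2%) vs 107/110 (97.3%) has Fisher p = 0.017, but the combined entry would be 204/220 = 92.7%.

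**4. Clustering, second-device use unrelated to outcome.** The share f of subjects using two devices and the within-subject correlation ICC are not in the documents; both are assumed. With one or two devices per subject:

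- design effect = 1 + ICC × 2f / (1 + f)
- actual error of a nominal 5% test = 2 × [1 − Φ(1.96 / √design effect)]

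| f | ICC | Design effect | Actual error |
|---|---|---|---|
| 0.05 | 0.1 | 1.01 | 5.1% |
| 0.10 | 0.3 | 1.05 | 5.6% |
| 0.20 | 0.5 | 1.17 | 7.0% |
| 0.50 | 0.5 | 1.33 | 9.0% |
| 0.50 | 0.8 | 1.53 | 11.4% |

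Simulation with 110 subjects per arm and 90% or 95% true success agrees: for example 6.7–6.9% in the third row and 11.0–11.2% in the last.

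**5. Clustering, second-device use driven by failure.** Assume first-device failure pf of 5% or 10% in both arms. A second device is opened in 80% of first-device failures and 20% of other subjects. Second-device failure probability is pf + ρ(1 − pf) after a failure and pf(1 − ρ) after a success. Devices per subject are 1 + 0.8 × 0.05 + 0.2 × 0.95 = 1.23, or 1 + 0.8 × 0.10 + 0.2 × 0.90 = 1.26. With the null true and 40,000 simulated trials per scenario, the device-level chi-square rejects in roughly:

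| ρ | Failure-driven second device | Second device in 20% at random |
|---|---|---|
| 0.05 | 5.3–5.7% | about 5% |
| 0.2 | about 7.5% | 5.5–6% |
| 0.5 | about 11% | about 7% |

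**6. Effect of the exact fallback in SAP 5.1.** Switching to Fisher's test when an expected count is below 5 (5,000 trials per scenario), at an assumed 2–3% failure, gives 1.7–4.7% in ten of twelve scenarios. The other two, failure-driven use with ρ = 0.5, give 6.1–8.0%. At 5–10% failure it gives 5.0–7.3%, except failure-driven use with ρ = 0.5 (10.7–11.3%).

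**The case against.** The strongest reply is that the comparison is already planned. SAP 5.4.2 names the endpoint as categorical on FAS and PPS, and 5.1 supplies a two-group test at two-sided 0.05. No sentence says to merge the arms, and the definition is per group. A statistician following the text would produce the comparison whatever the shell looks like. That stands. A reader of Table 32 might infer that the comparison is never made, or that the plan pools the arms; neither is supported. Pooling is the natural reading of a shell without arm columns, but a test-arm-only table is also possible, since the protocol's endpoint definition speaks of the investigational device. On either reading the shell cannot carry the comparison.

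A second reply is that the inflated error rests on assumptions. That also stands. A reader might infer that the error rate is certainly above 5%, or that a second device usually follows failure of the first. The documents give no frequency for second devices and no correlation. The endpoint is delivery, deployment and withdrawal, not recanalization, so a second device may follow one that operated correctly. With few failures, the exact fallback can leave the test conservative.

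Third, the consequence is limited. The pass/fail rule in protocol 8.2 uses only the primary confidence interval and safety. Tables 29–31 also give no rate difference or interval, so adding them here goes beyond the SAP's own pattern, and device-level cluster methods can be unstable with few failures. These points lower the weight of the finding and favour offering a subject-level option. They do not remove the mismatch between shell and text.

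**Conclusion.** The point holds as an inconsistency between the Table 32 shell and the rest of the plan, with an unspecified unit-of-inference problem behind it. The first part rests on the printed layout and needs no assumption beyond the table having been read correctly from the PDF.

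The second part is conditional. The independence assumption is not secured, because a subject may contribute more than one device. Under the assumed inputs the nominal 5% error is about 5–7% with unrelated second-device use in 20% of subjects and correlation up to 0.5. It reaches about 11% with failure-driven use and correlation 0.5, or with unrelated use in half of subjects and correlation 0.8. It may be negligible, or below 5%, if second devices or failures are few.

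This should be corrected before database lock. It concerns one secondary endpoint; the primary non-inferiority test and the 99/110/220 sample size are unaffected.

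**What to change.** - **Table 32:** split FAS and PPS into Experimental Group and Control Group as in Tables 29–31, and add Statistic and P-value rows, preferably with the rate difference and its 95% CI. Keep the per-device rate by arm as the descriptive figure.
- **SAP 5.4.2:** state one of two bases for the between-arm inference. Either work at subject level (for example first device used, or all devices successful) with a chi-square or exact test, or at device level with subject as the cluster (GEE, cluster-robust standard error or cluster bootstrap). The subject-level option is simpler and safer if failures are few.

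The cost is one table layout and one or two sentences. Protocol 6.2.1.3 already has the model of each device and the operation-success evaluation recorded at Visit 2, so no new data should be needed. A first-device definition additionally requires that the order of use can be identified. The statistical downside is a slightly wider interval than the naive one.
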